**Table 1. Overview of *NIE*'s 9-month multi-level, multi-component intervention plan.**

INDIVIDUAL	FAMILY	COMMUNITY	SYSTEMS
Native Stand (NS): 18-session school-based curriculum delivered twice a month over 9 months in NIE 's 5 participating schools. NS will be integrated into the schools' existing class schedules.	Native Voices (NV): 4 sessions delivered once every other month to students and parents/legal guardians after school hours at NIE 's 5 participating schools.	Cultural Mentoring Program (CMP): 9 mentoring sessions delivered twice a month over 9 months that include one group activity with CMP mentors and mentees and one 1:1 meeting. CMP activities will take place at varying locations on the Reservation depending on the activity.	SRH Services: Monthly meetings over 12 months with Epi Team at the Fort Peck Tribes Headquarters offices in Poplar, Montana.
NS 1: Introduction to an overview of NIE and Native Stand	NV 1: Introduction to an overview of NIE and Native Voices	CMP 1: Assiniboine/Sioux kinship networks and concepts of family and genealogy	Epi Team meetings will take place monthly over 9 months to enhance coordination and implementation of SRH services for AI youth.
NS 2: Culture & Tradition – Part 1		CMP 2: Traditional male/female roles and cultural beliefs about healthy relationships	
NS 3: Culture & Tradition – Part 2		CMP 3: Cultural beliefs about sex and how to make decisions about sex that integrate cultural values	
NS 4: Healthy Relationships – Part 1		CMP 4: Cultural beliefs about parenting and the role of family	
NS 5: Healthy Relationships – Part 2		CMP 5: The role of ceremony in traditional Assiniboine/Sioux culture	
NS 6: Reproductive Health – Part 1		CMP 6: The role of sweat lodges in AI spirituality	
NS 7: Reproductive Health – Part 2		CMP 7: Honoring ceremonies in the lives of young men and women	
NS 8: Pregnancy & Parenting		CMP 8: Understanding the sacredness of the land	
NS 9: Preventing Pregnancy		CMP 9: Buffalo Harvest	
NS 10: Condoms & Birth Control			
NS 11: Sexually Transmitted Diseases			
NS 12: HIV/AIDS & HCV			
NS 13: Drugs, Alcohol, & Sex	NV 3: Prevention of STIs, HIV/AIDS, and HCV		
NS 14: Mental Health & Sex			
NS 15: Negotiation & Refusal Skills			
NS 16: Decision-Making			
NS 17: Effective Communication			
NS 18: Putting It All Together			

completed treatment. ***Following randomization of the schools to the intervention, there will be three waves of implementation: Wave 1 (1 school in 2019), Wave 2 (2 schools in 2019-2020), and Wave 3 (2 schools in 2020-2021).*** The 5 schools on the Fort Peck Reservation will be the clusters that are randomized to *NIE*. *NIE* will take approximately 40 weeks, or 3 quarters, to implement. The first observation period (Q4 of Year 2) provides baseline measurements for all respondents drawn from every cluster. The cluster is then surveyed at 3, 9, and 12 months for the students in the cluster once they have begun participation in the intervention, and at 9 and 12 months for the parents/legal guardians in the cluster once they have begun participation in the intervention. Following completion of the intervention across all clusters, we will conduct the quantitative analysis. The SWD allows us to control for the effect of time and ensure that the full AI population of schools at Fort Peck receives *NIE*. The systems-level component of *NIE* will be implemented reservation-wide rather than school-wide during Years 2 to 4 of *NIE* as the SWD is rolled out. The systems level component will be measured and analyzed qualitatively.

**2.3.6 Trial Timeline.** The timeline for *NIE* is: Year 1-Refine, tailor, and finalize the components of *NIE* with the CAB by reviewing our current quantitative and qualitative data from Fort Peck and by talking with elders

[figure not shown]

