### SECTION 3: ANALYSIS PLAN

**3.1.1 Power analysis.** Sample size requirements were calculated taking into account a unique design effect for the SWD, such that  $N_{sw} = Nu \times DE_{sw}$  (where  $Nu$  is the total number of students needed to detect the treatment effect with a power of 80% and a significance level of 0.05, uncorrected for cluster and repeated measurements). The design effect was calculated as:

$$DE_{sw} = \frac{1 + \rho(ktn + bn - 1)}{1 + \rho\left(\frac{1}{2}ktn + bn - 1\right)} \times \frac{3(1 - \rho)}{2t(k - \frac{1}{k})}$$

where  $k$  is the number of steps,  $n$  is the expected number of students per cluster,  $b$  is the number of baseline measurements,  $t$  is the number of measurements after each step, and  $\rho$  is the intra-class correlation coefficient, estimated to be 0.016 based on findings reported by Kaufman et al. With an  $\rho$  of 0.05, power of 0.8,  $Nu = 292$ ,  $DE_{sw} = 1.3273$ , and the expectation of 15% attrition during the study, a sample size of 456 will allow the detection of a 0.14 increase in the proportion of condom use relative to the frequency of sexual intercourse from baseline to the 12-month observation period hypothesized under Aim 2.

**3.1.2 Missing data.** Attrition is likely to covary with truancy, suggesting a missing data mechanism that is not missing at random (NMAR). To address this, a dropout variable  $D_i$  will be developed for each individual across the 4 observation periods, where  $D_i=k$  for dropout between the  $(k-1)$  and  $k^{\text{th}}$  occasion. A model of the probability of dropout, where

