## SECTION 4: STUDY INTERVENTION ADMINISTRATION OF DATA COLLECTION

*NIE* is a mixed methods study involving quantitative and qualitative methodology. There are four data collection components to *NIE*: 1) student survey (quantitative); 2) parent survey (quantitative); 3) systems level tracking (qualitative); and 4) fidelity, acceptability and sustainability evaluation (qualitative). The student survey, parent survey and systems level tracking data collection are described in section 4.1. The fidelity, acceptability and sustainability evaluation data collection is described in section 4.2.

**4.1. *NIE* Intervention Components:** The intervention components and corresponding modes of data collection to test efficacy of the four aspects of our intervention are shown in the table below. The left column indicates the intervention component, while the right column indicates the type of data collection and the timeline of data collection.

Intervention Component	Types of Data Collection and Timeline
Individual level: Native Stand	
 
• Student Surveys: baseline, 3 months, 9 months, 12 months
 

Family level: Native Voices	
 
• Parent Surveys: baseline, 9 months, 12 months
 

Community level: Cultural Mentoring	
Systems level: Enhancement of the coordination and implementation of SRH services at Fort with the Fort Peck Epi Team	
 
• Barriers and Facilitators Discussion Group: yearly
 
• Coordination & Implementing Monitoring Plan Tracking Log: quarterly
 

Subsequent to randomization of the 5 area schools to the intervention, there will be a baseline data collection from the middle of March to June 2019, followed by three waves of implementation and concurrent data collection over the next 3 years. For a visual picture of how these intervention components and methods of data collection fit into an overall Timeline, please see our Trial Timeline in the appendix.

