From Years 2-4, 456 students and one of their parents/legal guardians will participate in *NIE*'s data collection. Student surveys for baseline, 3, and 9 months will be administered during regularly scheduled classes in an assigned classroom by [name], the assistant, and N/E's outreach coordinator. Baseline data collection will begin in March 2019 for all schools and parents included in the intervention. Groups of 20 students at a time will be appropriately spaced in the classroom in order to ensure privacy, and survey instructions will be presented to students prior to REDCap administration. [name], the assistant, and the *NIE* outreach coordinator will thoroughly review the assent form with the students, which will include a description of *NIE*, types of questions that will be asked, and potential risks and benefits of participating in *NIE*. All students will be reminded that they can withdraw at any time without consequences. Prior similar procedures have been successfully used by [name] and [name] for data collection in the Fort Peck schools with AI youth. For students who graduate from high school prior to the 12-month follow-up, they and their parent/legal guardian will be contacted by [name] to complete the 12-month follow-up (during evening hours) at the high school from which they graduated following the same procedure described above. Although data collection for the students has been designed to coincide with the school year, the same procedures will be followed if the data collection occurs when school is not in session.

Wave 1 data collection will commence in December 2019 with 1 school after students have begun receiving the Native Stand and Cultural Mentoring components of the intervention during the school year.

Wave 1 9- month follow-up will take place at the end of the school year in May/June 2020 as the intervention is completed. The Wave 1 12-month follow-up will take place at the beginning of the next school year in September 2020.

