Wave 2 (2 schools) and Wave 3 (schools) will follow the same procedures and pattern of timeline of data collection. The parent survey will be administered during evening hours at the high school by [name], the assistant, and N/E's outreach coordinator. All baseline parent data will be collected in Fall 2019. We will use the same REDCap administration procedures for parents/legal guardians that are described for students above. [name], the assistant, and the N/E outreach coordinator will review the consent forms with the parents/legal guardians to ensure their understanding of the purpose of N/E, types of questions they will be asked, and the study's potential risks and benefits. All parents/legal guardians will be reminded that they can withdraw themselves and/or their child at any time without consequences.

Wave 1 (parents of first school) parent 9- month follow up will take place in spring of 2020. Wave 1 parent 12-month follow-up will take place in Fall 2020. Wave 2 (parents of schools 2 and 3) and Wave 3 (parents of schools 4 and 5) will follow the same procedures and pattern of timeline of data collection. Data Safety & Monitoring Plan describes participant safety and support plans

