#### **4.1.2 For the systems-level component of N/E, there are 2 forms of data collection: a barriers/facilitators discussion guide, and a coordination and implementation monitoring plan tracking log.**

These 2 forms of data collection span the 8 service domains relative to improving SRH services for adolescents as outlined by the CDC. The barriers/facilitators discussion guide will be administered in a group discussion format to the Epi Team at baseline and at 12 months during a standing monthly meeting held at the Fort Peck Tribal Headquarters to assess the factors that impede or strengthen the provision of SRH services for AI youth at Fort Peck. The Epi Team's discussion of the barriers/facilitators will be recorded and transcribed. Based on findings from the barriers/facilitators guide, a coordination and implementation monitoring plan will be developed in the form of a tracking log, in order to monitor improved coordination and provision of SRH services. The coordination and implementation monitoring plan tracking log will be completed as part of the baseline data collection and tracked quarterly during a regular monthly meeting of the Epi Team. [name] and [name] will be the primary research staff-with assistance from two of N/E's consultants, [name] and [name] collaborate with the Epi Team in completing the barriers/facilitators discussion guide, developing the implementation monitoring plan, and tracking the plan's progress toward increasing access to SRH services for AI youth. No identifying data or participants will be collected.

**4.1.3 Incentives:** Incentives for the students and parents/legal guardians are based on discussions with N/E's Community Advisory Board and members of the FPCC research team, as well as [name] prior experience with research studies involving Indigenous communities. Students will receive \$10 at the baseline, 3-month, and 9-month data collections and \$20 at the 12-month data collection. Parents/legal guardians will receive \$10 at the baseline and 9-month data collections and at each of the 4 sessions of Native Voices, plus \$20 at the 12-month data collection. Similar incentives for students and parents have been previously successful. Epi Team members will not receive incentives for participation in N/E, as it is part of their tribal employment responsibilities.

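### On the visible schedule no school gives control data after the common baseline, so a 0/1 effect cannot be separated from categorical periods and time is not controlled as claimed

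*Combined protocol and SAP*

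**What the plan says.** Section 2.3.5 (Trial Design) sets a single starting round: "The first observation period (Q4 of Year 2) provides baseline measurements for all respondents drawn from every cluster". It continues: "The cluster is then surveyed at 3, 9, and 12 months for the students in the cluster once they have begun participation". It then draws the conclusion at issue: "The SWD allows us to control for the effect of time".

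The rest of the visible text follows the same schedule for students:

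- Section 4.1 plans "a baseline data collection from the middle of March to June 2019, followed by three waves of implementation". For the first school, "Wave 1 data collection will commence in December 2019 with 1 school after students have begun receiving" the programme, with later surveys in May/June and September 2020. Waves 2 and 3 "will follow the same procedures and pattern of timeline of data collection".
- Section 3.1.2 defines a dropout variable that "will be developed for each individual across the 4 observation periods".
- Section 4.1.3 pays students "at the baseline, 3-month, and 9-month data collections and" once more at 12 months, which makes four surveys.
- Table 2 has student columns for baseline, 3, 9 and 12 months only. Section 5.3.1 counts those months from the start of the intervention and ties the surveys to the student's own cluster's programme.

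The model in section 3.1.5 (Generalized linear mixed-effects models) has a fixed time effect indexed by j, an intervention term X coded 0/1 or as dose, with coefficient theta, and a random school effect. The period j is not defined. Section 3.1.1 bases N = 456 on a stepped-wedge design effect.

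**The concern.** A stepped wedge separates the intervention from calendar time because, in the same period, some schools have crossed over and others have not. If waiting schools are not surveyed, that comparison is missing. X is 0 only at the common baseline and 1 at every later survey, so any change since spring 2019 is a candidate for the intervention effect.

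Such change is likely. The students are 15 to 18 and grow older over the study, and COVID-19 falls inside the window. An IRB memorandum of 30 September 2020 approves data collection on the pandemic's impact on the primary outcome variables and on the stepped-wedge design. That collection covers a subset, by network survey and interview, and nothing visible makes it control data for the primary model.

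What is at stake is whether Aim 2 can be reported as a randomised, time-controlled effect, and whether the model as specified will run without the software dropping a term.

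**Working it through.** **1. The plan's own sample size.** 292 × 1.3273 = 387.6, and 387.6 / 0.85 = 455.97, so 456 reproduces. The printed design effect is

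DE = [1 + ρ(ktn + bn − 1)] / [1 + ρ(½ktn + bn − 1)] × 3(1 − ρ) / [2t(k − 1/k)].

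The documents do not state k, t, b or n. On an integer grid (k 2–5, t 1–4, b 0–2, n 1–619, ρ 0.016 or 0.05), 1.3273 appears only at k = 2, t = 1, b = 1, n = 71, ρ = 0.016:

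- first factor: (1 + 0.016 × 212) / (1 + 0.016 × 141) = 4.392 / 3.256 = 1.3489
- second factor: 3 × 0.984 / (2 × 1.5) = 0.984
- product: 1.3273

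At k = 1 the formula divides by zero. With k of at least 2, some school must be measured as a control after baseline.

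**2. Is theta estimable?** Build the 20 school-by-survey cells: five schools in waves of 1, 2 and 2, a baseline in May 2019, and surveys 3, 9 and 12 months after each start. None of the 15 post-baseline cells has X = 0. Theta is estimable only if adding X raises the rank of the period matrix.

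Wave starts are not fully dated, so three calendars were used: Sep 2019/Sep 2020/Sep 2021, Sep 2019/Jan 2020/Sep 2020, and Sep 2019/Jan 2020/Jan 2021. The first fits poorly with the wave dates in section 2.3.5, which put Wave 3 in 2020–2021. Six period widths were tried: survey round, calendar quarter, grant quarter, school year, grant year and calendar year.

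| Data used | Rank before and after X, survey rounds | Collinear combinations |
|---|---|---|
| All four surveys | 10 and 10 | 15 of 18 |
| Baseline plus 12 months | 4 and 4 | 18 of 18 |

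Fixed school effects do not help (14 and 14; 8 and 8). Each calendar contributes 5 of 6 and 6 of 6, so dropping the first leaves 10 of 12 and 12 of 12. The three exceptions are calendar-year periods (rank 4 to 5, or 3 to 4). They work by pooling the spring baseline with Wave 1's single December 2019 survey, so any outside change between those dates enters theta one for one.

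**3. What a linear calendar trend gives.** Assumed inputs:

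- SD = 0.14 / 2.80 × √(292/4) = 0.427, from Nu = 292 at 80% power, two-sided 0.05 (sidedness is not stated)
- 456 × 0.85 / 5 = 77.5 completers per school
- ICC 0.016, random school effect, normal reference
- detectable difference = 2.80 × SE

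| Data used | SE of theta | Detectable difference at 80% power | With within-student correlation 0.5 (assumed) |
|---|---|---|---|
| All four surveys | 0.051–0.055 | 0.14–0.16 | 0.11–0.12 |
| Baseline plus 12 months | 0.096–0.129 | 0.27–0.36 | 0.20–0.27 |

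The estimate leans on the assumed line. A one-off change between December 2019 and April 2020 passes into theta at 0.50–0.60 over four surveys, and at 1.00 with baseline plus 12 months.

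**4. Adding a step in early 2020.** Over four surveys the model is estimable (SE 0.062–0.064), but Wave 1's one December 2019 survey carries weight 1.00. Every 12-month survey falls in September 2020 or later, so for baseline plus 12 months the step equals X (rank 3 of 4 in all three calendars).

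**5. Size of the confounding.** The months from May 2019 to the 12-month surveys, averaged over schools, are:

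- (16 + 2×28 + 2×40)/5 = 30.4
- (16 + 2×20 + 2×28)/5 = 22.4
- (16 + 2×20 + 2×32)/5 = 24.0

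A before-after comparison would show the full 0.14 with no intervention effect if condom use drifted by 0.14 × 12 / 30.4 = 0.055 to 0.14 × 12 / 22.4 = 0.075 per year.

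**The case against.** The evidence is partly an absence. Figure 4 and the appendix timeline, the natural places for a waiting-school schedule, are not shown, and section 2.3.6 lists baseline collection among the activities of Years 2, 3 and 4. A reader might infer that the trial certainly has no concurrent controls. The documents do not support that; they support only a statement about the visible text. If the unseen sources do schedule such surveys, however, they contradict sections 2.3.5 and 5.3.1, and the text still needs correcting.

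Section 3.1.5 never says that time is categorical. The index j suggests it, but a reader should not infer that no effect can be fitted at all. A linear trend, calendar-year periods or individual dose each yield an estimate. The first rests on the line, the second on one school's December 2019 survey, and the third mainly on attendance, which is not randomised (section 3.1.3).

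It is also tempting to say that the detectable difference rises from 0.14 to 0.27–0.36. That holds only if the 3- and 9-month surveys are dropped, and no passage says they are. The appended registration record names 12 months for the primary analysis under H1, but lists 3, 9 and 12 months for the primary outcome measure.

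Finally, the arithmetic of 456 is not wrong. What lacks support is the stepped-wedge measurement pattern that its design effect assumes.

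**Conclusion.** The point stands for the visible schedule. With 0/1 X and one effect per survey round, theta is not estimable. Across the period definitions tried it is collinear in 15 of 18 combinations over all four surveys and in 18 of 18 for baseline plus 12 months. The time-control claim and the stepped-wedge design effect are therefore unsupported by that schedule, and any workable version is a before-after estimate that depends on an assumption about time. Section 3.1.1 itself describes the target as a change from baseline to 12 months.

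The rank result needs no numerical assumption beyond the survey dates. The standard errors rest on the inputs in step 3 and are optimistic: they count every completer, although the condom ratio exists only for students who had sex in the past month, and they use a normal reference with five schools. Confidence is moderate because of the unseen figure and timeline. The matter should be settled before analysis, because it changes what the trial can conclude.

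**What to change.** 1. Reconcile sections 2.3.5, 2.3.6 and 5.3.1 (with its participation requirements) with Figure 4 and the appendix timeline. State whether waiting schools are surveyed. Settle the baseline date: section 2.3.5 says Q4 of Year 2, section 4.1 says March to June 2019, and section 6.4.1 says Q2 of Year 2. Settle the primary time point between H1 and the registered outcome measure. Define the period j.
2. If waiting schools are not surveyed:
   - delete the claim that the design controls for time;
   - replace categorical periods with a pre-specified calendar-time trend plus age, fitted to all four surveys;
   - label any dose analysis as non-randomised;
   - report Aim 2 as a before-after estimate that depends on the assumed trend;
   - withdraw the stepped-wedge power claim.

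   A sensitivity model with an early-2020 step should either be omitted or be labelled as resting essentially on one school's December 2019 survey and unavailable for baseline plus 12 months.
3. Optional: survey waiting schools in the same round as a school already on the intervention. This restores estimability (rank 10 to 11 with survey rounds). It needs extra rounds, tracing of leavers and an IRB amendment, and some rounds may already be past.

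Items 1 and 2 cost only wording and model specification. Their price is a weaker stated conclusion.
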